### 3.3.1.2.3. Adherence to sampling protocols

The proportion of participants who complete 100% of the expected assessments over the duration of the study.

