### 2.2.2. Secondary Objectives

- To assess differences in drop-out rates between the participants allocated to the retrospective assessment strategy (i.e., EPDS), and those allocated to the retrospective plus momentary assessment strategy (i.e., EPDS complemented with the EMA of mood, sleep, energy, enjoyment and worry).
- To assess differences in participants' adherence to sampling protocols between a retrospective assessment strategy (i.e., EPDS), and a retrospective plus momentary assessment strategy (i.e., EPDS complemented with the EMA of mood, sleep, energy, enjoyment and worry). We will achieve this by comparing the proportion of participants in each group that complete 100% of the expected assessments.
- To assess differences in usage patterns of the app between a retrospective assessment strategy and a retrospective plus momentary assessment strategy, including additional voluntary self-reporting, time spent using the app, number of interactions with other sections of the app, time to complete the self-assessments, and other ancillary usage data
- To assess differences in participants' acceptance of the app between a retrospective assessment strategy and a retrospective plus momentary assessment strategy through a post-study self-administered questionnaire

- To assess differences in timeliness of data collection between a retrospective assessment strategy and a retrospective plus momentary assessment strategy. We will achieve this by comparing the proportion of participants completing their assessments in response to a prompt displayed on their mobile devices between the two groups
- To assess differences in data completeness between a retrospective assessment strategy and a retrospective plus momentary assessment strategy. We will achieve this by comparing the proportion of complete records between the two groups
- To evaluate the impact of a momentary assessment technique of the EPDS scores by comparing the EPDS scores obtained at the start of the sampling period and the EPDS scores obtained at the end of this period. This will be assessed in the *retrospective plus momentary assessment* condition only
- To assess if feedback provided by a healthcare practitioner influences participants' and clinicians' engagement, acceptance and perceived usefulness of an app used for the remote and longitudinal monitoring of mood symptoms throughout pregnancy

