### 3.3.1.2.2. Drop-out rates

The proportion of participants who stop completing the retrospective or the retrospective plus momentary assessments before the end of the study (i.e., before 6 months). For those participants taking part in the app through a BYOD approach, we will consider they have dropped out if they miss 2 consecutive assessments. In this case, a notification on their phones will ask them to complete a question about the reason for not completing the assessments.

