### 3.5.2.2.1. Retrospective assessment

Participants in this condition will be asked to complete the EPDS once a month for 6 months. The day on which participants are required to complete the EPDS will be selected at random from each calendar month, and with no less than 2 weeks in between 2 consecutive sampling periods. On that day, we will select a random time between 10.00 and 22.00 to administer the EPDS. At that time, a notification will be displayed on a participant's phone asking her to complete the EPDS. They will then be able to accept the request or reject it. Outside the sampling period, participants will be allowed to complete as many assessments as they wish to. However, during the sampling period, participants will not be allowed to complete any additional assessments.

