### 3.5.2.2.2. Retrospective plus momentary assessment

Participants in this condition will be required to complete a sampling period of 4 consecutive days once a month for 6 months; this period will be randomly selected from each calendar month, with no less than 2 weeks in between 2 consecutive sampling periods. The sampling period will start on day 1 with an administration of the EPDS and will conclude with another administration of the EPDS on day 4. In between (i.e., days 1 to 4 of the sampling period) participants will be asked to complete EMA assessments on mood, sleep, energy, enjoyment and worry plus 2 contextual information questions 3 times a day. The sampling hours will run between 10.00 and 22.00. This 12-hour window will be divided into 3 periods of 4 hours each, and with no less than one hour in between 2 consecutive assessments. Participants will receive a notification prompting them to complete the assessment at random times within each 4-hour period. Participants will have the option to accept or reject the request in the notification. Outside the sampling period, participants will be allowed to complete as many assessments as they wish to. During the sampling period however, participants will not be allowed to complete any additional assessments.

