#### *3.8.2.9. Adherence to sampling protocols*

We will compare the proportion of participants who completed 100% of the expected assessments between the experimental groups using a t-test.

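### The between-arm adherence comparison sets completing all of 6 assessments against all of 84; it needs a companion comparison on the EPDS that both arms share

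*Combined protocol and SAP*

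**What the plan says.** Adherence is all-or-nothing for each woman. Section 3.3.1.2.3 gives the endpoint: "The proportion of participants who complete 100% of the expected assessments over the duration of the study". Section 2.2.2 sets the objective of assessing the difference between strategies by "comparing the proportion of participants in each group that complete 100% of the expected assessments", and section 3.8.2.9 compares the "proportion of participants who completed 100% of the expected assessments between the experimental groups using a t-test".

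The two schedules differ greatly in length.

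- **Retrospective arm** (section 3.5.2.2.1): "Participants in this condition will be asked to complete the EPDS once a month for 6 months".
- **Retrospective plus momentary arm** (section 3.5.2.2.2): a four-day sampling period each month for six months. Each period "will start on day 1 with an administration of the EPDS and will conclude with another administration of the EPDS on day 4". On days 1 to 4 there are also EMA ratings "plus 2 contextual information questions 3 times a day".

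The unit of an assessment is not defined. Section 3.5.2.2.2 treats each prompt as one, since prompts are spaced "with no less than one hour in between 2 consecutive assessments". The drop-out rule in section 3.3.1.2.2 uses the word without a unit: "we will consider they have dropped out if they miss 2 consecutive assessments".

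Adherence is a secondary objective and section 2.2.3 states no hypothesis for it. Section 3.6 sizes the study on the precision of the adherence rate in each arm.

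**The concern.** Completing everything is harder when there are 84 items than when there are 6, even if women behave identically at each prompt. A lower rate in the momentary arm is therefore expected from the schedule alone.

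The Background (section 1) raises the worry that EMA may overburden women and reduce engagement and response quality. That worry prompts two questions which this contrast cannot answer: do women respond less often per prompt, and does adding EMA cost completed monthly EPDS? A reader could take the p-value as evidence on either.

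No other planned endpoint fills the gap:

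- Data completeness (3.3.1.2.5) uses complete plus attempted records, so prompts never opened drop out of the denominator.
- Timeliness (3.3.1.2.4) is taken over each arm's own assessments.
- Drop-out (3.3.1.2.2) applies one rule of two consecutive misses to both schedules.
- The EPDS-impact objective (2.2.2) concerns scores, within the momentary arm only.

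**Working it through.** **The plan's own figure.** Reading the interval of 10 in section 3.6 as ±10 points: n = 1.96² × 0.5 × 0.5 / 0.10² = 96.04. The stated 96 per arm reproduces. It is a per-arm precision target.

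**Assessment counts.** Retrospective: 6 × 1 = 6. Momentary: 6 × (2 EPDS + 4 days × 3 EMA) = 6 × 14 = 84, of which 72 are EMA.

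**Assumptions.** The documents give no compliance rate and no within-woman correlation, so both are assumed ranges. Mean compliance m per assessment is set equal in both arms. Each woman's own probability follows a beta distribution with a = m(1−ICC)/ICC and b = (1−m)(1−ICC)/ICC. Then P(all n completed) = B(a+n, b)/B(a, b). The rejection column is for a pooled t-test on the yes/no outcome, 96 per arm, two-sided 5% (the plan states no level for this test).

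| m | ICC | All 6 | All 84 | Significant |
|---|---|---|---|---|
| 0.90 | 0.2 | 66% | 27% | about 100% |
| 0.90 | 0.8 | 86% | 80% | 18% |
| 0.95 | 0.2 | 82% | 52% | 99% |
| 0.95 | 0.3 | 84% | 64% | 91% |
| 0.95 | 0.5 | 88% | 78% | 51% |
| 0.95 | 0.7 | 91% | 86% | 20% |
| 0.95 | 0.8 | 93% | 90% | 12% |
| 0.99 | 0.2 | 96% | 88% | 57% |
| 0.99 | 0.8 | 98.5% | 97.9% | 4% |

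The gap never reverses under equal compliance, but it shrinks sharply as ICC rises.

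**Other readings of the schedule.**
- If EMA ran on days 2 and 3 only, the count would be 6 × (2 + 2 × 3) = 48. At m = 0.95 and ICC 0.2 that gives 82% versus 58%. The text says days 1 to 4, so 84 is the stated count.
- If the unit is a monthly period, a period holds 1 task against 14. At m = 0.95 the chance of completing one period in full is 95% versus 72% (ICC 0.2) to 92% (ICC 0.8).

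**Can the planned test see lost EPDS?** Assume 95% EPDS compliance in the retrospective arm, 90% EMA compliance, and a correlation of 0.8 between a woman's EPDS and EMA propensities. At ICC 0.3, full completion in the momentary arm is 41% if its EPDS compliance stays at 95% and 37% if it falls to 90%. Against 84% in the retrospective arm, the test is significant in almost every trial either way. At ICC 0.8 it is significant in about 81% of trials without the fall and 92% with it.

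**What the shared comparison would give.** With 6 EPDS against 6 day-1 EPDS and equal compliance, both arms have the same expected rate. At m = 0.95 and ICC 0.2 to 0.8, the half-width of the 95% CI for the difference is:
- per-woman proportion: 1.96 × √[2 × m(1−m)(1+5×ICC)/(6 × 96)] = 4 to 6 points;
- all 6, with P the all-6 rate: 1.96 × √[2P(1−P)/96] = 7 to 11 points.

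The first day-1 EPDS precedes any EMA, so EMA can affect only the other five. With the first held at 95%, and each woman keeping the same propensity rank, all-6 power at ICC 0.2 / 0.3 / 0.5 / 0.8 is:
- fall from 95% to 90%: 58% / 53% / 43% / about one third;
- fall from 95% to 85%: 97% / 95% / 90% / 77%.

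**The case against.** The strongest reply is that the comparison answers the question asked. The schedule is the randomised intervention, and heavier prompting is part of the momentary strategy, not a confounder. Fewer women finishing an 84-item schedule is a real feasibility result. This stands. A reader might infer that the planned test is invalid or should be withdrawn; section 2.2.2 does not support that, because full completion of each schedule is its stated objective.

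It is also fair that the burden worry does not rest on this test alone. Section 2.2.2 plans comparisons of drop-out, usage patterns and acceptance, and item 7 of Appendix 4 asks women whether they were asked to report too often. None of these measures scheduled EPDS completed out of EPDS due.

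The size is driven by assumptions, which also stands: the probability of a significant result runs from about 4% to 100% over the ranges tried. Equal compliance is itself an assumption, since a ten-item EPDS and a short EMA prompt need not be completed equally often.

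Finally, the shared comparison has limits. Later day-1 EPDS fall at least two weeks after the previous sampling period, and the day-4 EPDS, which follows the EMA most closely, has no counterpart in the other arm. A null result on day-1 EPDS would not rule out burden within a sampling period.

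**Conclusion.** The point holds as a gap in interpretation. The planned contrast measures full-schedule completion, and any difference in it includes the 6 versus 84 prompt count. It does not isolate response per prompt or completed monthly EPDS. The direction follows from equal per-assessment compliance. The size could be large (82% versus 52% at 95% compliance and ICC 0.2) or negligible (98.5% versus 97.9% at 99% and ICC 0.8), and the documents do not say where between these the study would fall.

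Two further inferences are not supported. One is that a significant result is bound to occur: at high ICC it is not. The other is that the sample size is undermined: section 3.6 rests on each arm's own rate, which the schedule imbalance does not touch. Because adherence is secondary, has no stated hypothesis and feeds no decision rule, this is a worthwhile improvement and not a fatal flaw.

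**What to change.** 1. Keep the 100% comparison in sections 2.2.2, 3.3.1.2.3 and 3.8.2.9. Label it full-schedule completion and state that it includes the 6 versus 84 prompt count.
2. Define whether an assessment is a prompt or a monthly period, there and in section 3.3.1.2.2.
3. Pre-specify a second between-arm comparison on the shared component: the 6 scheduled EPDS in the retrospective arm against the 6 day-1 EPDS in the momentary arm. Report the per-woman proportion completed and the proportion completing all 6, each as a difference with 95% CI. Keep all randomised women in the denominator and count missed or withdrawn assessments as not completed.
4. Show EPDS completion by month, so that the first, pre-EMA EPDS can be seen separately.
5. Report day-4 EPDS and EMA compliance separately within the momentary arm.

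The cost is wording plus one more secondary analysis. The 100% definition already requires knowing which EPDS each woman completed, so no new data are collected. Given the limited all-6 power for a small effect, the confidence interval should lead and the p-value should not.

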### 3.3.1.2.4. Timeliness of data collection

Each pre-specified assessment will be preceded by a prompt. Timeliness of data collection will be defined as the proportion of participants who complete the pre-specified assessments immediately after receiving this prompt.

### 3.3.1.2.5. Data completeness

The implementation of validation procedures will prevent users from leaving unanswered questions. However, they will be able to terminate the current assessment (leaving a log trail of this). Therefore, data completeness is the proportion of assessment records with complete answers out of the total number of complete plus attempted records.

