#### 3.6. Sample size

According to Matthey (2004), the minimal clinically significant difference for the EPDS (calculated using a reliable change index (RCI) and a standard deviation of 4) is 4 points. Therefore, for the study using tablet computers in antenatal clinics, in order to demonstrate a one-sided equivalence between the two layouts (i.e., scrolling versus paging) of the EPDS using an additive model (i.e., the mean score difference between the two groups not exceeding 3 points) with an alpha level of 0.025, power of 0.80 and a standard deviation of 4 we would need 126 participants. In addition, in order to demonstrate the PPV, PNV and FOR of the Whooley questions we would need at least 30 events (i.e., women scoring 10 points or higher on the EPDS). Assuming a prevalence of depression in pregnant women of 12%, we would need to recruit 250 participants. For these reason, we will aim to recruit a total sample of at least 300 participants.

For the app through a BYOD approach study, we aim to determine adherence to sampling protocols. We have chosen to relate the proposed sample size to the 95% confidence interval for the rate, as recommended by the Research Design Service in London. Therefore, we would need 96 participants in each arm with a 95% confidence level and a confidence interval of 10. This translates into a total sample of 192 (i.e., 96 participants in each experimental group). For this reason, we will aim to recruit at least 200 participants.

For the additional condition where participants will receive feedback from a designated member of the clinical care team, we aim to recruit 30 participants.

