#### *3.8.2.6. Data completeness*

We will compare the proportion of complete records between the experimental groups using a t-test.

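### App-study data completeness is counted in records, but women are randomised; the only stated test makes no allowance for repeated records from one woman

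*Combined protocol and SAP*

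**What the plan says.** All references are to the combined protocol and SAP.

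- Definition (3.3.1.2.5, app study): "data completeness is the proportion of assessment records with complete answers out of the total number of complete plus attempted records". Unanswered questions are blocked by validation, so an incomplete record is one that the woman terminated.
- Objective (2.2.2, app study): differences in completeness are assessed by "comparing the proportion of complete records between the two groups".
- Test (3.8.2.6): "We will compare the proportion of complete records between the experimental groups using a t-test". The section does not say whether it covers the tablet study, the app study or both.
- Schedule, retrospective arm (3.5.2.2.1): "Participants in this condition will be asked to complete the EPDS once a month for 6 months".
- Schedule, retrospective plus momentary arm (3.5.2.2.2): women "complete a sampling period of 4 consecutive days once a month for 6 months". Each period is to "start on day 1 with an administration of the EPDS and will conclude with another administration of the EPDS on day 4", and on each of its days the EMA items are asked "plus 2 contextual information questions 3 times a day".

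Adherence and timeliness (3.3.1.2.3, 3.3.1.2.4, 3.8.2.9, 3.8.2.10) are counted in participants. Of these three app-study endpoints, only completeness is counted in records. Section 3.8 gives no per-woman summary, mixed model, GEE or cluster-robust variance.

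**The concern.** The randomised unit is the woman (3.1, 3.5.2.2, 3.7). Whether an assessment is finished or abandoned plausibly depends in part on who is answering, so records from one woman are likely to be correlated. A t-test with records as observations ignores this and uses too small a standard error. Variation between women could then be reported as an effect of the assessment strategy. The unequal schedules make this worse: an arm with 84 scheduled records per woman appears far more informative than its number of women warrants.

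The arms also differ in what a record is. In the retrospective arm every scheduled record is a ten-item EPDS. In the other arm most are short EMA forms of five items plus two context questions (Appendices 2 and 3). A difference in the overall proportion may therefore partly reflect the length of the form.

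**Working it through.** **The plan's own figure.** Section 3.6 says "we would need 96 participants in each arm with a 95% confidence level and a confidence interval of 10". Reading this as ±10 percentage points around a proportion of 50%: n = 1.96² × 0.5 × 0.5 / 0.10² = 96.04. The figure reproduces. It is set for adherence, which has one value per woman.

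**Scheduled records per woman.**
- Retrospective: 1 EPDS × 6 months = 6.
- Retrospective plus momentary: (2 EPDS + 4 days × 3 EMA) × 6 months = 14 × 6 = 84, of which 12 are EPDS and 72 are EMA (72/84 = 86%).
- Per arm, with 96 women: 96 × 6 = 576 and 96 × 84 = 8,064.

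**Variance.** Let ICC be the correlation between two records of the same woman, taken as equal in both arms. The design effect is 1 + (m − 1) × ICC, that is 1 + 5 × ICC and 1 + 83 × ICC. With equal true completeness in the arms, the ratio of true to assumed variance of the difference is

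[(1 + 5 × ICC)/576 + (1 + 83 × ICC)/8,064] / [1/576 + 1/8,064].

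The coefficient of ICC is (5/576 + 83/8,064) / (1/576 + 1/8,064). Multiplying top and bottom by 8,064 gives (70 + 83)/(14 + 1) = 10.2, so the ratio is 1 + 10.2 × ICC.

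**Actual error of a nominal two-sided 5% test** = 2 × [1 − Φ(1.96 / √(1 + 10.2 × ICC))].

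| ICC | Design effects | Variance ratio | Error by formula | Error by simulation |
|---|---|---|---|---|
| 0 | 1, 1 | 1.00 | 5.0% | 5.0–5.3% |
| 0.01 | 1.05, 1.83 | 1.10 | 6.2% | 6.0–6.2% |
| 0.05 | 1.25, 5.15 | 1.51 | 11.1% | 10.8–11.3% |
| 0.10 | 1.50, 9.30 | 2.02 | 16.8% | 16.9–17.0% |
| 0.20 | 2.00, 17.6 | 3.04 | 26.1% | 25.8–26.5% |
| 0.30 | 2.50, 25.9 | 4.06 | 33.1% | 32.3–33.2% |

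The simulation is beta-binomial, with 10,000 trials per setting, 96 women per arm, the scheduled counts, and true completeness of 80%, 90% or 95% in both arms. The ranges run over those three levels.

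**With the woman as unit.** One proportion per woman, compared by a Welch t-test in the same simulated trials, gives an error of 4.8% to 5.6% across all settings.

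**EPDS records only.** With 6 against 12 records per woman the coefficient is (10 + 11)/(2 + 1) = 7. The error is still 9.2% at ICC 0.05 and 13.3% at ICC 0.10, so leaving out the EMA records would not remove the problem.

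**The case against.** **The plan never says that records are pooled.** This is the strongest reply, and it stands in part. A reader might infer that the plan prescribes a t-test on pooled records. The documents do not go that far: they give a ratio and name a t-test, without naming the unit of analysis. The ratio could be computed for each woman, and a t-test on those values would be sound. Still, definition, objective and test all speak of records while the neighbouring endpoints speak of participants. Records as the unit is therefore the natural reading, and the sound alternative is not written down.

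**Section 3.8.2.6 may belong to the tablet study.** It sits among tablet-study items, and section 2.1.3 uses similar wording for the two EPDS layouts. There each woman gives one EPDS record, so no clustering arises. If it covers only that study, the app-study comparison in 2.2.2 has no stated test. The section needs amending either way.

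**6 and 84 are not limits on the denominator.** Correct. They are scheduled counts. Prompts can be rejected, women drop out, and voluntary assessments are allowed outside sampling periods; 3.3.1.2.5 does not exclude them. The table holds for the scheduled counts. Because it gives every woman in an arm the same count, it cannot show how far frequent reporters would dominate.

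**EMA records may be meant to count.** A reader might infer that the comparison should be confined to EPDS records. The documents do not support this: 2.2.2 compares whole strategies, and the Background raises EMA burden as a concern.

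**The endpoint is minor.** It is secondary, and section 2.2.3 states no hypothesis for it. That limits the consequence but does not make the test valid.

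**Conclusion.** The concern holds on the natural reading of the plan. If records are the unit, the test understates the variance of the difference by a factor of 1 + 10.2 × ICC. The false-positive rate of a nominal 5% test rises to about 6% at ICC 0.01, 17% at 0.10 and 33% at 0.30.

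This rests on scheduled counts, 96 women per arm, one ICC common to both arms, and a two-sided 5% level. The documents give no ICC and no significance level for the app-study tests; the 0.025 in section 3.6 belongs to the tablet-study equivalence calculation. The direction holds for any ICC above 0, and at ICC 0 there is no inflation.

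The effect is confined to one secondary comparison. A reader might infer that the app-study sample size is also undermined. It is not, because it was set for adherence, which is counted per woman.

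**What to change.** In 3.3.1.2.5 and 3.8.2.6, state which study each provision covers and that the app-study comparison takes the woman as the unit of analysis. Choose one method in advance:

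- a completeness proportion for each woman, compared by a Welch t-test (the arms will differ in variance because the record counts differ); or
- a logistic GEE or mixed model on records, clustered on woman.

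State also whether voluntary assessments and rejected prompts enter the denominator, and how a woman with no attempted record is handled, since her proportion is undefined.

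Keep the whole-strategy comparison. Alongside it, report EPDS and EMA completeness separately as a description, because most scheduled records in the momentary arm are short EMA forms.

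The cost is revised wording, a little more analysis work, and wider but correct intervals for this comparison. No new data, change of design or larger sample is needed.
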